Patients and study coordinators will enter baseline demographic, gout history, patient reported outcomes (PROs) directly into electronic case report forms into a 21CFR and HIPAA compliant REDCap (Nashville, Tennessee) system. We will host REDCap on one of several access-controlled, encrypted servers housed at UAB. Subsequent PROs and other outcome data will be captured by phone in the same REDCap database by the study teams. Baseline laboratory data and medication data will be obtained from our respective EMRs and will be reviewed during the phone calls and by the research assistant during the ED visit.

B.8 Study Outcomes

Study outcomes (**Table 2**) will be collected from patients at 6 weeks and 3 months following the initial ED visit with questionnaires deployed using computer assisted telephone interviews (CATI) programmed in REDCap. Validated items about gout flares and gout medications have been used in the past by our team.⁸⁴

B.8.1 Primary outcomes Aim 1 and 2.

The primary outcome of aim 1 will be the ability of the alert to successfully identify gout patients. For aim 2, it will be the proportion of patients that have a follow-up visit addressing gout in the 3-month period after the ED visit. Many gout patients are not adherent with their follow-up visits due to a lack of awareness of the consequences of untreated

gout, poor care access, and/or inadequate assistance to obtain a follow up visit. Even rapidly-scheduled outpatient visits (next business day) following an ED encounter are only attended by 73% of those seen in a recent study and rates of post-ED follow-up for many chronic disease are closer to 50%.^{91, 92} Moreover, most patients, ~80%, leave the ED with knowledge deficits that impact adherence and outcomes.^{93, 94} Having a usual source of primary care and establishing continuity of care after an ED visit is critical to optimal disease outcomes in all chronic diseases including gout.³⁰⁻³² This data will be captured both by self-report on surveys (this will be the primary study outcome) and by review of EMR data within our respective healthcare systems. While self-report will be impacted by recall and possible social desirability bias, this should be non-differential (bias towards the null).⁹⁵ EMR data will be more accurate for some outcomes but will miss any gout care delivered outside our urban Southeastern medical centers and their satellite facilities.

B.8.1.1 Secondary outcomes - Aim 2

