Outcome ascertainment	X			X	X
Study debriefing				X	
Assess AEs			X	X	X

[°]Primary outcome assessment will occur at any point upto 6 weeks post ED visit dependent on routine care visit; # For individuals randomized to navigation arm; ^{\$}Navigator will contact participant in the week prior to scheduled follow-up visit

B.9.1.6 **Blinding and Unblinding**

Participants will blinded to study assignment at enrollment, and following primary outcome ascertainment will be debriefed regarding the study and its purpose/goals.

B.10 Statistical Analysis Plan

B.10.1 Primary Outcome Analysis - Aim 1.

All analyses will adhere to the principles of rigor, reproducibility and transparency.^{109, 110} To determine the effectiveness of our alert system, we will examine the diagnostic properties (sensitivity/specificity) of the EMR alerts against a gold standard of NLP/ML detection (section C.4.2)

B.10.2 Primary Outcome Analysis- Aim 2.

Descriptive statistics, including measures of central tendency (means for continuous, proportions for categorical) and dispersion (variance, interquartile range) will summarize the distribution of baseline characteristics of randomized patients seen in both EDs. Descriptive statistics will be summarized by treatment arm as well as enrollment site. These statistics will inform the successfulness of randomization in creating comparable groups and ascertain our success in recruiting the populations we seek to target (particularly under-represented minorities). We also will compare the descriptive characteristics between those participants who do and don't respond to follow-up surveys to detect and report any evidence of a selective non-response bias. The primary analysis approach for testing treatment effect will be a multivariable logistic regression

model. We have chosen multivariable logistic regression over Cochran-Mantel-Haenszel approaches to allow for effect estimation of multiple covariates (race, gender, age) upon the primary outcome and to allow tests of interactions. Logistic regression models, including interaction terms, will be developed for 6 week outcomes and 3 month outcomes. We will examine the significance of the effects of the intervention as the outcome of persons receiving at least one outpatient gout follow-up visit at 3 months. We will analyze rates on an intent-to-treat basis for the primary analysis. We will conduct all analyses using SAS 9.4 (Cary, NC)

[figure not shown]

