B.10.3 Secondary Outcome Analyses- Aim 2.

Patient reported outcomes (PROs) and other process of care measures are of key interest in this study. We will examine secondary outcomes using either two-sample t-tests or multiple linear regression models. Distributional assumptions for residuals (normality, homogeneity of variance) will be examined using normal probability plots and residual plots. We will conduct a set of stratified analyses (contrasts) to examine how the between-site differences in approaches affect outcomes. First, comparing across control arms at the four sites we can estimate the impact of the intervention. Second, comparing across intervention arms at the four sites, we can estimate the difference attributable to case manager versus navigators when all individuals receive story telling. We will also examine sex as a biological variable as well as effects of age and race/ethnicity (heterogeneity of treatment effect). We will conduct sensitivity analyses using multiple imputations to account for missing data. While we provide an example sample size for one such measure, the evaluation of these endpoints will be hypothesis-generating only.

B.11 Sample Size Considerations for Aim 2

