The funding announcement we are responding to seeks to improve care and reduce healthcare disparities for chronic disease in the Southeast. Thus, our approach to this study is to maximize the number of patients we can evaluate and improve gout care outcomes. We based our sample size considerations on experience from prior ED interventions, a pilot study conducted at UAB (section C.3.5) aimed at recruiting minority patients for our CORT Registry and Biorepository, based on a prior diagnosis of gout in the UAB EMR, and experience recruiting clinic patients. Annually in the ED, UAB see approximately 720 and 450, gout patients (with primary or secondary diagnoses), respectively. We anticipate identifying approximately 60% of these patients using the alert in real-time ($n = 702$). We also estimate that 80% of the ED physicians will respond to the ED alert and activate the gout order set and referral to the study coordinator (this rate may be improved with approaches discussed in section C.4.4) ($n = 560$). Based on the results of our UAB pilot study (that contacted patients without a known recent flare/acute gout), we anticipate that 50% of these patients will remain eligible (based on medical record review and questionnaire). Thus, we conservatively estimate randomizing a combined total of approximately 280 gout patients annually between UAB. Despite plans to offer compensation for survey completion, we anticipate a 30% rate of survey non-response for the primary outcome at 3 months ($n = 196$, in the per protocol analysis), which we believe will be slightly disproportionate between those receiving the intervention vs. control arm. Based on a sample size of 200 patients and assuming 2:1 randomization in favor of story-telling, the study will have 80% power to detect relative risks of 1.68 or below using a two-tailed Type I error rate of 0.05, assuming the proportion in the control arm scheduling an outpatient primary care or specialist visits targeted for gout within 3 months is above 30% (Figure 4). We picked these rates of visit follow-up visits to represent the range of rates of ED follow-up within 3 months for other conditions such as asthma, stroke, and diabetes. ¹¹¹⁻¹¹⁵

Figure 4. Power for Study Aim 2

C. Adverse Events

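### The primary analysis is called intent-to-treat, but it is sized on survey responders and has no rule for the 30% expected to lack a 3-month self-report

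*Combined protocol and SAP*

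**What the plan says.** B.8.1 defines the Aim 2 primary outcome as the "proportion of patients that have a follow-up visit addressing gout in the 3-month period after the ED visit". Of its two sources it says: "This data will be captured both by self-report on surveys (this will be the primary study outcome". The EMR is the second source, and B.8.1 warns that it "will miss any gout care delivered outside our urban Southeastern medical centers".

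B.10.2 analyses this outcome by multivariable logistic regression and says "We will analyze rates on an intent-to-treat basis for the primary analysis". It also promises a comparison of baseline characteristics between survey responders and non-responders.

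B.10.3, on secondary outcomes, adds: "We will conduct sensitivity analyses using multiple imputations to account for missing data".

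B.11 expects to randomise about 280 patients (section D gives 168 + 112 = 280) and says "we anticipate a 30% rate of survey non-response for the primary outcome at 3 months". It places the remaining 196 "in the per protocol analysis), which we believe will be slightly disproportionate between those receiving the intervention vs. control arm". Its power statement uses 200 patients, 2:1 allocation, a control rate of 30% and an RR of 1.68, "using a two-tailed Type I error rate of 0.05".

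**The concern.** Self-report is the primary outcome, so a missing 3-month survey is a missing primary outcome unless the plan says otherwise. It does not. A logistic model omits records with no outcome, so the plan run as written gives a responder-only result carrying an intent-to-treat label. Scoring non-responders as no visit is another common reading of an intent-to-treat rate. The two readings give different power and can give different effect estimates.

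The choice matters because B.11 itself expects the arms to respond at different rates. The design offers a plausible reason: navigators telephone intervention patients (B.5.2, B.9.1.2), and no such calls are described for controls. Under no-visit scoring, a response gap alone creates an arm difference. Under responder-only analysis a gap alone does no harm. Bias arises if answering is related to keeping a visit, and differently so in the two arms. Left open, the rule could be chosen after outcomes are seen.

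**Working it through.** **Inputs.** From B.11: control rate 0.30; RR 1.68, so intervention rate 0.30 × 1.68 = 0.504; 2:1 allocation; two-sided 0.05; N = 200 in the power statement; 280 randomised; 30% non-response, so 280 × 0.70 = 196 answer and 84 do not. The arm-specific non-response rates below are assumptions, because B.11 gives neither size nor direction.

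**Formula** (unadjusted two-proportion test, c = control, t = intervention):

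- p̄ = (n_c·p_c + n_t·p_t)/(n_c + n_t)
- s0 = √[p̄(1 − p̄)(1/n_c + 1/n_t)]
- s1 = √[p_c(1 − p_c)/n_c + p_t(1 − p_t)/n_t]
- power = Φ[(|p_t − p_c| − 1.96·s0)/s1]

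**1. The plan's own figure.** N = 200 (66.7 and 133.3): p̄ = 0.436, s0 = 0.0744, s1 = 0.0709. Power = Φ[(0.204 − 0.1458)/0.0709] = Φ(0.82) = 79.4%. At N = 196 it is 78.6%. The stated 80% reproduces.

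**2. All 280, equal 30% non-response, missing scored as no visit.** Rates become 0.30 × 0.70 = 0.210 and 0.504 × 0.70 = 0.353. The RR stays at 1.68, but the difference falls from 20.4 to 14.3 points. s0 = 0.0584, s1 = 0.0548. Power = Φ[(0.1428 − 0.1144)/0.0548] = Φ(0.52) = 69.8%.

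**3. All 280, every outcome recovered at the responder rates.** 0.30 vs 0.504, s0 = 0.0629, s1 = 0.0599. Power = Φ[(0.204 − 0.1232)/0.0599] = Φ(1.35) = 91.1%. This is the ceiling.

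**4. A 6-point gap, overall non-response still 30%, missing scored as no visit, N = 280.** Each arm's rate is multiplied by (1 − its non-response). Both splits average 30% at 2:1: (34 + 2 × 28)/3 = 30 and (26 + 2 × 32)/3 = 30.

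| Non-response, control / intervention | Rates if true RR is 1.68 | RR | Power | Rates if no effect (both 30%) | RR | False positives |
|---|---|---|---|---|---|---|
| 34% / 28% | 0.198 vs 0.363 | 1.83 | 82% | 0.198 vs 0.216 | 1.09 | 6.1% |
| 26% / 32% | 0.222 vs 0.343 | 1.54 | 55% | 0.222 vs 0.204 | 0.92 | 6.6% |

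False positives are two-sided rejections in either direction.

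**5. Do other provisions supply the rule?**

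- The responder/non-responder comparison in B.10.2 describes selective response but does not handle it.
- Multiple imputation in B.10.3 is a sensitivity analysis placed under secondary outcomes. Whether it reaches the primary outcome is unclear, and either way it is not the primary rule.
- EMR review in B.8.1 has no substitution rule.
- Repeat calls, secondary contacts, email and text (B.9.1.3, D.2) reduce missingness but do not say how to treat what remains.

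**The case against.** The best defence is that B.10.2 means analysis by assigned arm, and that B.11 does what most plans do: it discounts the number randomised to the number expected to have outcomes. That stands as far as the sample size goes. A reader might infer that the 80% is wrong, or that a true per-protocol primary analysis competes with the intent-to-treat one. The documents support neither. The 80% reproduces, and the 196 are defined by answering a survey, not by adherence, so the label is a misnomer. What remains is the missing rule.

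A reader might also infer serious inflation of the false-positive rate. No-visit scoring with 25% non-response under intervention and 40% under control would give about 13%, but a 15-point gap goes well beyond what B.11 calls slight. At 6 points the rate is 6% to 7%. Nor does no-visit scoring always cost power: if controls are the poorer responders, it rises to 82%.

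Finally, 84 is an upper bound. Table 2 collects the primary outcome at week 6 as well as month 3, and a visit reported at week 6 already meets the endpoint. Some other visits will be in the EMR. The plan does not say that either source settles the outcome, so this reduces the size of the problem without removing it.

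**Conclusion.** The point holds as a gap in the primary analysis, not as an error in the power calculation. The plan names intent-to-treat, sizes the endpoint on responders, expects uneven non-response, and gives no rule for patients who do not answer. With equal non-response, power for the same inputs is about 70%, 79% or up to 91%, depending on the rule. Under no-visit scoring, a 6-point gap moves a true RR of 1.68 to 1.83 or 1.54, and a null effect to 1.09 or 0.92. Up to 84 of 280 patients are affected, fewer if week-6 or EMR visits count.

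These figures assume that the planned 30% and 50.4% apply to responders. They also take 200 to be the 196 rounded, use assumed 34/28 and 26/32 splits, and rest on an unadjusted test rather than the covariate-adjusted model. The plan does not support a claim that the trial will be biased by any particular amount or in a particular direction.

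**What to change.** **In B.10.2:**

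- Define the primary set as all randomised patients, analysed by assigned arm.
- Count a visit already reported at week 6 as meeting the endpoint.
- Multiply impute the remaining missing 3-month self-reports separately by arm, using baseline covariates, the week-6 answer where there is one, and the EMR-recorded gout visit. The EMR visit is auxiliary information, not a substitute for self-report, because B.8.1 says the EMR misses outside care.
- Report two sensitivity analyses: 3-month responders only, and missing scored as no visit.

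**In B.11:**

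- Replace the per-protocol label with survey responders.
- Say that the 80% applies to about 200 observed outcomes.
- State that power under imputation lies between about 79% (nothing recovered beyond the responders) and 91% (everything recovered), provided missingness is ignorable given the variables in the imputation model.

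The cost is SAP wording and modest extra analysis work. The plan already collects all the inputs. The rule should be fixed before outcomes are examined by arm.

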- 1) *Gout medical care*- Self-reported flare rates will be captured using the Gaffo gout flare criteria (developed and validated at UAB) and adapted to self-report.^{79, 84} Uptake of evidence-based gout care will include self-reported prescribing rates of ULT and opioid analgesics. We also will determine medication adherence based on participant self-report. Since obesity is a major factor associated with gout and weight reduction will be addressed in the stories (as well as how to avoid foods high in purines), we will examine changes in self-reported weight between study entry and follow-up.
- 2) *Healthcare resource utilization*- outcomes will include repeat ED visits (ED recidivism) and re-hospitalization rates. Outpatient visits to primary care and/or rheumatologists will be measured as the primary outcomes.
- 3) *Health-related Quality of Life (HRQL), Shared Decision Making and Perception* – HRQL will be recorded using the European Quality of Life (EQ-5D) scale⁸⁶⁻⁸⁸. We will use the CollaboRATE scale, a brief patient survey focused on shared decision making, to measure perception of shared decision making from a patient perspective.⁹⁰

B.8.1.2 Key Covariates Aim 2. To better describe the population we are studying and to adjust for any potential imbalances that might not be addressed by randomization, we will collect key social determinants of health as covariates at baseline and for dynamic measures, again at month 3. These will include: health literacy,¹⁰³ economic factors, transportation, discrimination and other key demographics such as educational level, community social economic status, and personal measure of socioeconomic status will be assessed using measures from the Behavioral Risk Factor Surveillance System.¹⁰⁸ We will also capture the time of “stories” watched as a measure of dose-response of the intervention.

B.9 Study procedures and Assessments

B.9.1.1 Screening, Enrollment, and Randomization (see Step-By-Step Guide in Appendix)

Following the gout alert activation in the ED, research assistants housed in the UAB ED will interview patients in person to further determine possible eligibility, and if potentially eligible, to consider randomization. Patients classified as having acute gout based on the Gaffo criteria who meet the inclusion/exclusion criteria will be

Table 2. Specific Aim 2 Outcomes and Covariates

	ED	WK 6	Mo 3	Time Point
Primary Outcome				
Outpatient primary care or specialist visits targeted for gout*		X	X	

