Secondary Outcomes / Covariates				
Social Determinants of Health				
Environmental and social factors	X			
Gout medical care				
Number of gout flares (Gaffo criteria) ^{79, 84}	X	X	X	
Rates of urate lowering therapy (ULT)**	X	X	X	
ULT adherence		X	X	
Opioid prescriptions*	X	X	X	
Weight reduction		X	X	
Healthcare resource utilization (visit number)				
ED visits (indicative of recidivism)*		X	X	
Hospitalizations*		X	X	
Health-related quality of life				
European Quality of Life (EQ-5D) ⁸⁶⁻⁸⁸	X	X	X	
Shared decision making: CollaboRATE scale ⁹⁰		X	X	

* gout follow-up within 3-months of ED visit. ** Assessed through chart or system review

randomized 2:1 stratified by race/ethnicity, to the intervention (storytelling +/- patient navigation) or control arm (usual care). All intervention arm patients in the UAB ED also will be assigned lay navigators to provide personalized support for care transitions and access to post-gout flare medical services needed for preventing recurrent flares.

The following procedures will be completed during the index ED visit:

- Review inclusion/exclusion criteria for registry participation
- Informed Consent
- Review of current/past gout status and medication chart review
- Pain Assessment
- Laboratory
 - Serum uric acid (from chart review)
 - Sample banking
- Survey assessments
 - HRQL
 - SDOH

Laboratory draw will be done in conjunction with ED care blood draw when possible. At the conclusion of visit, participants randomized to navigator arm will be provided navigators picture, contact information, and informed that they will receive a call w/in 72 hours.

B.9.1.2 *Patient Navigator Contact*

72 hours post ED visit

During this initial phone conversation the navigators will: 1) conduct a baseline assessment to identify barriers to attending an outpatient visit for gout care (e.g. transportation) and to adhering to gout treatment recommendations (medications, diet, exercise) and, 2) determine the level of support and assistance (e.g. transportation support) needed by patient. The patient navigator will help facilitate the follow-up visit with a primary care/gout specialist, identify any barriers (e.g. lack of trust in primary care physician or/and healthcare system), and provide institutional/community resources that can be mobilized for the patient.

4 weeks post ED visit and 24-48 hours prior to appointment (anticipated)

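### B.10.3 gives every Aim 2 secondary outcome a t-test or linear regression, though five of nine are counts or yes/no; under 2:1 allocation, equal-variance intervals are then too narrow or too wide when the arms differ

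*Combined protocol and SAP*

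**What the plan says.** The only method sentence in B.10.3 for the Aim 2 secondary outcomes is "We will examine secondary outcomes using either two-sample t-tests or multiple linear regression models". It is followed by a diagnostic: "Distributional assumptions for residuals (normality, homogeneity of variance) will be examined using normal probability plots and residual plots". The section does not say what happens if those plots are unsatisfactory, or whether the t-test is the pooled or the unequal-variance form. It plans multiple imputation as a sensitivity analysis and adds that "the evaluation of these endpoints will be hypothesis-generating only".

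Table 2, leaving aside the social-determinant covariates, lists nine secondary items:

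- Counts: flares ("Number of gout flares (Gaffo criteria"), and ED visits and hospitalizations under the heading "Healthcare resource utilization (visit number".
- Yes/no: ULT use and opioid prescriptions, which B.8.1.1 describes as "self-reported prescribing rates of ULT and opioid analgesics".
- Scores or measurements: weight change, EQ-5D and CollaboRATE.
- No scale stated: ULT adherence.

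Section B.9.1.1 has patients "randomized 2:1 stratified by race/ethnicity", and B.11 confirms that the larger arm is the intervention. Logistic regression appears only in B.10.2, under the primary outcome: "Logistic regression models, including interaction terms, will be developed for 6 week outcomes and 3 month outcomes".

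**The concern.** For a yes/no outcome or a count, the variance is tied to the mean. If the intervention changes the mean it also changes the variance, so the arms have unequal variances exactly when there is an effect to estimate. Equal allocation largely hides this; 2:1 allocation does not. An equal-variance standard error gives more weight to the variance of the larger arm, whereas the true standard error of the difference depends more on the smaller arm. If the control arm has the larger variance, the interval is too narrow. If it has the smaller variance, the interval is too wide.

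The planned diagnostic does not help. Residuals from a yes/no outcome cannot be normal, so the normality check fails by construction, and no response is specified. The analyst would have to choose a model after seeing the data. B.10.3 calls the patient-reported and process measures of key interest, and B.1 puts lower utilization and less opioid use in the overarching goal. Readers will therefore rely on these estimates and intervals.

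**Working it through.** **The plan's own figure.** B.11 gives numbers for the primary outcome only: 80% power at N = 200, 2:1, control rate 30%, relative risk 1.68 (intervention rate 0.30 × 1.68 = 0.504), two-sided 0.05. The standard two-proportion formula with a pooled null variance gives 79.4%, so the figure reproduces. Nothing comparable is stated for the secondary outcomes.

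**Inputs.** Allocation is 2:1. B.11 expects 280 × 0.70 = 196 respondents at 3 months, taken as 131 intervention and 65 control. Event rates, mean counts and dispersion for the secondary outcomes are not in the documents. They are assumptions here and are shown over a range.

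**Formula.** Write Vc and Vi for the control and intervention variances, with n control and 2n intervention patients.

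- Pooled: SE² = [(2Vi + Vc)/3] × [1/n + 1/(2n)] = (2Vi + Vc)/(2n)
- True: SE² = Vi/(2n) + Vc/n = (Vi + 2Vc)/(2n)
- Ratio of pooled to true SE: r = √[(2Vi + Vc)/(Vi + 2Vc)]
- Approximate coverage of a nominal 95% interval: 2Φ(1.96 r) − 1

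The variance is p(1 − p) for a proportion, m for a Poisson count, and m + m²/k for an overdispersed (negative binomial) count with shape k.

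**Three examples.**

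- Yes/no, 30% to 20%: r = √(0.53/0.58) = 0.956, coverage 93.9%.
- Poisson mean 1 to 0.5: r = √(2.0/2.5) = 0.894, coverage 92.0%.
- Yes/no, 20% to 35%: r = √(0.615/0.5475) = 1.060, coverage 96.2%.

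**Simulation.** The runs used 131 against 65 patients, with 60,000 replicates (40,000 for the row marked *). Pooled means a pooled t-test or ordinary least squares. Welch means the unequal-variance t-test.

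| Control → intervention | r | Pooled | Welch |
|---|---|---|---|
| Yes/no 30% → 20% | 0.956 | 93.9% | 95.1% |
| Yes/no 30% → 15% | 0.922 | 92.9% | 95.0% |
| Yes/no 10% → 5% | 0.902 | 91.6% | 94.1% |
| Yes/no 50% → 25% | 0.953 | 94.0% | 95.1% |
| Yes/no 60% → 40% | 1.000 | 95.1% | 95.1% |
| Yes/no 80% → 60% | 1.069 | 96.6% | 95.0% |
| Yes/no 20% → 35% (a rise) | 1.060 | 96.2% | 94.8% |
| Poisson 1 → 0.75 | 0.953 | 93.9% | 94.9% |
| Poisson 1 → 0.5 | 0.894 | 92.1% | 95.0% |
| Overdispersed, k = 0.5, 1 → 0.75 | 0.926 | 93.1% | 94.3% |
| Overdispersed, k = 0.5, 2 → 1 | 0.834 | 89.4% | 93.9% |
| Overdispersed, k = 0.5, 0.3 → 0.1 * | 0.816 | 88.1% | 93.0% |

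With no difference between arms, pooled coverage was 94.7-95.3%. In a separate 40,000-replicate run on counts (means 0.2-0.6 against 0.1-0.3), a log-link rate ratio with robust standard error covered 94.5-95.8%.

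**Pattern.** For counts, and for proportions below 50%, a fall in the intervention arm makes the pooled interval too narrow, and more so with larger effects and stronger overdispersion. Starting from about 50% the error is small. Starting well above 50% it reverses. A rise in a proportion that stays below 50% makes the interval too wide.

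**The case against.** A reader might infer that the stated method always gives intervals that are too narrow when the intervention reduces events. The documents do not support that, for four reasons.

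- B.10.3 does not say the t-test is pooled. The unequal-variance version restores coverage to about 93-95%. The defect therefore belongs to a pooled t-test or to ordinary linear regression without a robust standard error. The second is one of the two named methods, so the point survives.
- The direction depends on the starting rate. The only background figure for a secondary outcome is opioid prescribing in over 50% of ED encounters (A.1). It is not a follow-up rate, but near it the pooled interval is about right: 94.7% for 55% to 40%. A flat claim that opioid intervals are too narrow is unsupported. For ULT, which the trial aims to increase, the likely error is an interval that is too wide.
- The worst figures need reductions of 50-67%, the very worst with strong overdispersion as well. At 25-33% the loss is one to two points.
- There is no type I error inflation, and the plan declares these endpoints hypothesis-generating, so no confirmatory claim depends on them.

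All four stand as limits on size. It is also fair that a mean or risk difference is a legitimate estimand; the linear scale itself is not the fault. It might be argued that the logistic sentence in B.10.2 covers the secondary outcomes too, since it speaks of outcomes at both time points. It sits under the primary analysis, however, and B.10.3 has its own method statement. None of this supplies a binary or count model, or a response to failed residual plots.

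**Conclusion.** The concern holds in a limited form. That five of nine secondary outcomes are given only linear methods, with a normality check that must fail for yes/no data and no stated response, follows from the text and needs no assumed rate. The numerical consequence is modest, runs in both directions, and applies only to equal-variance standard errors:

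- about 93-94% coverage for 25-33% reductions in counts or in proportions below 50%;
- about 88-92% for most 50-67% reductions, lowest with strong overdispersion; among yes/no outcomes, 30% to 15% gives 92.9% and 50% to 25% gives 94.0%;
- about 95% for reductions from just above 50%;
- about 96% for a rise from 20% to 35%.

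These figures assume 131 and 65 respondents and the event rates and dispersions shown, none of which come from the documents. The primary analysis is not affected. The change is worth making because it costs almost nothing and removes a model choice that would otherwise be made after seeing the data.

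**What to change.** Replace the single method sentence in B.10.3 with one rule per outcome type:

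- Yes/no outcomes (ULT use, opioid prescription): logistic or modified Poisson regression, reported as a risk difference or risk ratio.
- Counts (flares, ED visits, hospitalizations): negative binomial regression, or Poisson with a robust standard error, with log follow-up time as offset.
- EQ-5D, weight change and other scores: keep the linear model.
- Any mean difference: unequal-variance t-test, or a robust standard error in regression.

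State the scale of ULT adherence so that it falls under one of these rules, and say what will be done if the residual plots for the linear models are unsatisfactory.

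The cost is SAP wording and standard procedures in the SAS 9.4 already specified. It needs no new data and no extra patients.
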